#### **1.2.1.5 Safety of Vemurafenib**

The safety evaluation of vemurafenib is based on results in patients from three Genentech clinical pharmacology studies (Study NP22676, n=25; Study NP25163, n=52; and Study NP25158, n=7), a Phase I study (Study PLX06-02, n=108; Vemurafenib IB), a single-arm, Phase II study in previously treated patients with *BRAF*V600 mutation–positive Stage IV melanoma (Study NP22657, n=132; Vemurafenib IB), and a Phase III, randomized, open-label, multicenter, global study in patients with unresectable Stage IIIC or Stage IV *BRAF*V600 mutation–positive melanoma (Study NO25026, n=675; Vemurafenib IB). The type and incidence of adverse events observed across all studies in patients with *BRAF*V600 mutation–positive unresectable or metastatic melanoma were consistent.

In the clinical pharmacology Study NP25163, all 52 patients (100%) had at least one adverse event. Nearly all patients (96%) had at least one treatment-related adverse event. The majority of adverse events were of mild or moderate intensity. The most common adverse events (reported in  $\geq 30\%$  of patients) in the vemurafenib group were fatigue (58%), arthralgia (58%), nausea (50%), rash (38%), and diarrhea (33%). Fifty-four percent of patients had at least one Grade  $\geq 3$  adverse event; 40% of patients had at least one treatment-related adverse event. The most commonly reported treatment-related adverse events (incidence  $\geq 5\%$ ) were squamous cell carcinoma (SSC) of skin (23%), increased gamma glutamyl transferase (GGT; 9%), basal cell carcinoma (BCC; 7%), rash (7%), maculopapular rash (6%), and arthralgia (6%). Twelve patients (23%) experienced at least one Grade 4 adverse event, including 2 patients who experienced two Grade 4 adverse events. Five of the 12 patients had Grade 4 adverse events that were assessed by the investigator as treatment related. The most frequent Grade 4 adverse event was increased GGT (n=5 patients, assessed as related to treatment in 4 patients). The other Grade 4 adverse events were hyperuricemia (assessed as related to treatment) and pneumonia, sepsis, convulsion, pseudomonas infection, staphylococcal infection, multi-organ failure, and pulmonary embolism (all of which were assessed as unrelated to study treatment).

Study PLX06-02 (Vemurafenib IB) assessed the safety of escalating doses of vemurafenib. At the highest dose administered (1120 mg BID), dose-limiting rash (National Cancer Institute Common Terminology Criteria for Adverse Events [NCI CTCAE] Grade 3) and fatigue (Grade 3) were observed in multiple patients. Vemurafenib doses of up to 960 mg BID (the MTD) were generally well tolerated.

In the Phase II clinical trial (Study NP22657; Vemurafenib IB), all patients experienced at least one adverse event, the most common of which were arthralgia (68%), fatigue (57%), rash (54%), photosensitivity (52%), nausea (42%), alopecia (38%), pruritus (32%), diarrhea (32%), skin papilloma (31%), and hyperkeratosis (30%). Seventy-three percent of patients experienced at least one Grade  $\geq 3$  adverse event. Sixty-one percent of patients had at least one Grade  $\geq 3$  treatment-related adverse event. The most commonly reported, treatment-related adverse events (incidence  $\geq 5\%$ ) were *squamous cell carcinoma* (SCC) of skin (23%), increased serum GGT (9%), BCC (7%), rash (7%), maculopapular rash (6%), and arthralgia (6%). The Vemurafenib IB summarizes the Grade 3 or 4 study drug-related adverse events observed in Study NP22657.

In the Phase III randomized study of vemurafenib versus DTIC (BRIM-3, Study NO25026, clinical cutoff: 1 March 2011; Vemurafenib IB), the safety results showed that vemurafenib was generally tolerable and toxicity was manageable with dose modifications. Ninety-nine percent and ninety-one percent of patients in the vemurafenib and DTIC treatment groups, respectively, experienced at least one adverse event. The majority of adverse events were of mild or moderate intensity. The most common adverse events (reported in  $\geq 30\%$  of patients) in the vemurafenib group were in the system organ class of skin and subcutaneous tissue disorders; the most common

of which were alopecia, rash, and photosensitivity. Other adverse events that occurred in  $\geq 10\%$  of vemurafenib-treated patients and at an incidence of more than twice that observed in the DTIC group included SCC of skin, skin papilloma, arthralgia, headache, dysgeusia, pyrexia, peripheral edema, pain in extremity, myalgia, decreased appetite, diarrhea, hyperkeratosis, seborrheic keratosis, and dry skin. Of the 37 patients who switched from DTIC to vemurafenib, 32 patients (86%) had at least one adverse event and 26 patients (70%) reported at least one treatment-related adverse event. The majority of adverse events were of mild or moderate intensity.

Fifty-nine percent of patients in the vemurafenib arm and thirty-three percent of patients in the DTIC arm experienced one or more adverse events of Grade  $\geq 3$  in intensity. Treatment-related adverse events of Grade  $\geq 3$  occurred in 49% of patients in the vemurafenib arm and 20% in the DTIC arm. Sixteen percent and nine percent of vemurafenib-treated patients had cutaneous squamous cell carcinoma (cuSCC) and keratoacanthoma (KA), respectively, compared with  $< 1\%$  and 0% for DTIC-treated patients. For reporting purposes, all cases of cuSCC and KA were considered to be treatment related, Grade 3, and serious. Other common Grade  $\geq 3$  adverse events in the vemurafenib group included photosensitivity reaction (9%), rash (8%), maculopapular rash (8%), and arthralgia (4%); the corresponding frequency of these adverse events in the DTIC group were 0%, 0%, 0%, and  $< 1\%$ . The most common Grade  $\geq 3$  adverse event in the DTIC group was neutropenia, occurring in 9% of patients;  $< 1\%$  of patients in the vemurafenib group experienced neutropenia. Of the 37 patients who crossed over from DTIC to vemurafenib, 11 (30%) experienced one or more Grade  $\geq 3$  adverse event after crossover. These events consisted of fatigue (2 patients), muscle weakness, pyrexia, anemia, hyperkeratosis, BCC, maculopapular rash, rash, cellulitis, palmar-plantar erythrodysesthesia syndrome, and decreased neutrophil counts (all 1 patient each). Of these, eight events were considered by the investigator to be treatment related.

The percentage of patients who experienced one or more Grade 4 adverse event was lower in the vemurafenib group (13 patients [4%]) than in the DTIC group (22 patients [8%]). Grade 4 adverse events in the vemurafenib group included pulmonary embolism (3 patients), increased GGT (2 patients), increased blood creatine phosphokinase (CPK), increased blood bilirubin, increased lipase, ageusia, intraventricular hemorrhage, pneumonia, pneumothorax, respiratory distress, and neutropenia (1 patient each). Five patients treated with vemurafenib had a total of six Grade 4 adverse events that were assessed as related to treatment (increased blood bilirubin, GGT increased [2 patients], ageusia, increased CPK, and neutropenia). One of the 37 patients who crossed over experienced a Grade 4 decreased neutrophil count after crossover. It was assessed as unrelated to treatment and non-serious.

Grade 5 adverse events were reported in 6 patients (2%) in the vemurafenib group. Only one adverse event (intracranial tumor hemorrhage) was assessed as treatment related. Each of the other 5 patients experienced the following Grade 5 adverse events

(all unrelated to study treatment): general physical health deterioration, cerebrovascular accident, pneumonia, aortic aneurysm rupture, and cardiac failure. Grade 5 adverse events were reported in 8 DTIC-treated patients (3%). Fatigue and mucosal inflammation, initially classified as Grade 5 adverse events in 1 patient, were subsequently considered to be symptoms of disease progression and downgraded to Grade 1, resulting in a total of 7 patients with Grade 5 adverse events. Only one adverse event (shock) was assessed as treatment related. Dyspnea, lung infection, cardiac arrest, and cardiac tamponade were reported in 1 patient each, and cardiopulmonary failure was reported in 2 patients. No Grade 5 adverse events were reported in the 37 patients who crossed over from DTIC to vemurafenib.

cell population upon stimulation with a BRAF inhibitor, an effect that was reversed upon addition of MEK inhibitor. Further, the cells exhibited dose-dependent and reversible activation of extracellular-signal-regulated kinase (ERK) in the *NRAS*-mutated leukemic clone. A second case of progression of a preexisting *RAS*-mutated malignancy (pancreatic adenocarcinoma with *KRAS* mutation) was reported with vemurafenib in 2014. On the basis of its mechanism of action, vemurafenib may cause progression of cancers associated with *RAS* mutations. Vemurafenib should be used with caution in patients with a prior or concurrent cancer associated with *RAS* mutation. Full details are provided in the current Vemurafenib IB.

In a Phase I trial (Study CA 184161, sponsored by Bristol-Myers Squibb), asymptomatic Grade 3 increases in transaminases and bilirubin occurred with concurrent administration of ipilimumab (3 mg/kg) and vemurafenib (960 mg BID or 720 mg BID) (Ribas et al. 2012). All liver laboratory abnormalities were asymptomatic and reversible with permanent discontinuation of the study drugs or, in some cases, administration of corticosteroids. On the basis of these data, concurrent administration of ipilimumab and vemurafenib is not recommended outside of a clinical trial. Full details are provided in the current Vemurafenib IB.

An analysis of liver-related adverse events reported with vemurafenib use showed that 63 cases (out of an estimated exposure of approximately 20,000 patients) of medically confirmed serious adverse events were consistent with drug-induced liver injury on the basis of clinical chemistry criteria from the Drug-Induced Liver Injury Expert Working Group (Aithal et al. 2011). Of the 63 cases, two were assessed as severe; both were reported as hepatic failure, and the outcomes of both cases are considered resolved. There were no reported deaths among the 63 cases of liver injury. The median time to onset of the adverse events was 44 days after initial dose. The median ALT to alkaline phosphatase (ALP) ratio was calculated as 1.5, suggesting a trend toward cholestatic pattern of liver injury. The analysis did not reveal any risk factors or populations at risk.

A review of the Roche safety database found neutropenia to be an uncommon (6 cases per 1000 person-years, 0.6%) adverse drug reaction associated with the use of vemurafenib, typically occurring during the first 6–12 weeks of treatment. Neutropenia appeared to be reversible, usually within 2 weeks, with temporary interruption, dose reduction, or discontinuation of vemurafenib and, in some cases, was managed with granulocyte colony–stimulating factor (GCSF).

The effects of vemurafenib on the QT interval were investigated as part of the Phase II Study NP22657 (Vemurafenib IB). This was not a “thorough” QT study as defined by health authorities because vemurafenib cannot be administered to healthy volunteers and it was not feasible to administer a positive or negative control to patients with metastatic melanoma. However, the centrally read ECG data obtained in triplicate at serial, time-matched points before and after dosing met the regulatory expectations for robust assessment of oncology therapeutics on the QT interval. The maximum

absolute corrected QT (QTc) values at any point after dosing were as follows: >450 millisecond (ms), 49 patients (37.1%); >480 ms, 6 patients (4.5%); >500 ms (Grade 3), 2 patients (1.5%). One patient (0.8%) had a maximal QTc increment >60 ms (Grade 2) compared with baseline. The upper boundary of the one-sided 95% CI for mean QTc prolongation reached a maximum of 17.7 ms on Day 105 of study treatment, based on measurements in 90 patients. Mean QTc interval prolongation closely tracked with the mean vemurafenib steady-state concentration over time. None of the QT prolongation events were serious or led to premature withdrawal from treatment or dose modification/interruption; none were clearly associated with prolongation of cardiac repolarization, arrhythmia, or any other cardiac function disorder. Additional information on the relationship between vemurafenib exposure and QT interval prolongation may be found in the Vemurafenib IB.

As of Q2 2014, an adverse drug reaction of pancreatitis has been identified in patients treated with vemurafenib. Seventeen cases of pancreatitis with no strong risk factors or alternative explanations were reported. Eight of the seventeen cases were assessed as likely associated with vemurafenib use on the basis of event onset latency and rechallenge/dechallenge information. The clinical presentation including mild to moderate severity was consistent with the clinical picture of drug-induced pancreatitis (Lankisch et al. 1995).

As of Q4 2014, an adverse drug reaction of potentiation of radiation treatment toxicity has been identified in patients treated with radiation either prior, during, or subsequent to vemurafenib treatment. This is based on twenty cases of radiation injuries, adjudicated as radiation recall (n = 8) and radiation sensitization (n = 12). The nature and severity of the events in all 20 cases were evaluated as worse than expected for the normal tissue tolerance to therapeutic radiation with fatal outcome in 3 cases. The reaction was seen in the skin, esophagus, lung, liver, rectum, and urinary bladder. Vemurafenib should be used with caution when given concomitantly or sequentially with radiation treatment. Full details are provided in the current Vemurafenib IB.

*Acute kidney injury, including interstitial nephritis, has been observed in patients treated with vemurafenib. The majority of these cases have been characterized by mild to moderate increases in serum creatinine (some observed in the setting of dehydration events), with recovery after dose modification. Serum creatinine will be monitored throughout the study. Vemurafenib acute kidney injury dose modification guidelines should be used when applicable, and it is recommended to routinely monitor serum creatinine levels in all patients undergoing vemurafenib therapy.*

*Dupuytren's contracture and plantar fascial fibromatosis have been reported with vemurafenib. The majority of cases were Grade 1 or 2, but severe, disabling cases of Dupuytren's contracture have also been reported.*

For a review of serious adverse events and adverse events that led to discontinuation of study treatment, consult the Vemurafenib IB.

See the Vemurafenib IB and/or prescribing information for additional details on nonclinical and clinical studies.

### **1.3 STUDY RATIONALE AND BENEFIT-RISK ASSESSMENT**

This is an open-label, multicenter, non-randomized study to provide continued access to vemurafenib for eligible patients with *BRAF*V600 mutation–positive malignancy (including metastatic melanoma and other cancer types) who were previously enrolled and treated in an antecedent vemurafenib study protocol without meeting the protocol’s criteria for disease progression or are being treated beyond progression and still deriving clinical benefit, as assessed by investigator.

Safety evaluations will be conducted during the study. Safety evaluations will begin on Day 1 of the study, and safety will continue to be monitored throughout the study until 28 days after the last dose of study drug. Adverse events related to the study drug will be monitored until resolution.

In summary, these patients have limited alternative treatment options and may potentially benefit from continued treatment with vemurafenib. Therefore, the potential benefits of participating in this study outweigh the potential associated risks.

## **2. OBJECTIVES**

### **2.1 PRIMARY OBJECTIVE**

The primary objective of this study is to provide continued access to vemurafenib for eligible patients with *BRAF*V600 mutation–positive malignancy who were previously treated in an antecedent vemurafenib protocol and did not meet the protocol’s criteria for disease progression or are being treated beyond progression and still deriving clinical benefit, as assessed by investigator, and may potentially benefit from continued treatment with vemurafenib.

### **2.2 SECONDARY OBJECTIVE**

The secondary objective is to collect and describe safety and tolerability data for patients who continue vemurafenib treatment in this extension (rollover) study.

## **3. STUDY DESIGN**

### **3.1 DESCRIPTION OF STUDY**

#### **3.1.1 Overview**

This is an open-label, multicenter, non-randomized study to provide continued access to vemurafenib for eligible patients with *BRAF*V600 mutation–positive malignancy who were previously enrolled and treated in an antecedent vemurafenib protocol and did not meet

the protocol's criteria for disease progression or are being treated beyond progression and still deriving clinical benefit (as assessed by the investigator) and may therefore potentially benefit from continued treatment with vemurafenib. *The maximum number of days between the last dose of study drug in the antecedent protocol and first dose in this extension (rollover) study will be 15 days.* Results of the study completion visit or other visit in the antecedent protocol may be used as screening/baseline for this extension (rollover) study. Screening/baseline is combined into one visit if completed within time intervals, as specified in Section 4.5.2.1 and Appendix 1. The first vemurafenib treatment in the extension (rollover) study will be recorded as Cycle 1, Day 1. Patients will receive treatment with oral vemurafenib at 960 mg BID, 720 mg BID, or 480 mg BID, depending on the last dose in the antecedent protocol. Treatment will continue until progression of disease or as long as the patient is deriving clinical benefit, as judged by the investigator (case-by-case decision with approval of the Medical Monitor), death, withdrawal of consent, unacceptable toxicity, loss to follow-up, or decision of the Sponsor to terminate the study, whichever occurs first.

One cycle is defined as 28 days. Clinic visits will occur on Day 1 of Cycles 1–7 and on Day 1 of every other cycle through Cycle 15. Then, for patients still receiving treatment, clinic visits will occur on Day 1 of every third cycle (i.e., screening/baseline and Day 1 of every third cycle from Cycle 18+ [see Appendix 1] for patients with  $\geq 17$  cycles of vemurafenib on an antecedent study) until unacceptable toxicity or disease progression, as defined by the investigator. In patients with measurable disease, tumor assessments will be conducted for purposes of evaluating whether treatment should be discontinued via routine tumor assessments (CT/magnetic resonance imaging [MRI]) consistent with institutional standards of care, as outlined in the Schedule of Assessments (see Appendix 1).

Tumor assessments as specified and conducted in the antecedent protocol, including any evaluable and measurable disease, will have been documented at screening in the antecedent protocol. In the extension (rollover) study, tumor assessments, including radiological tumor assessments of chest, abdomen, and pelvis (C/A/P) for measuring extent or progression of disease (CT scan is the preferred method) will be done at the discretion of the investigator according to local institutional standard of care for purposes of evaluating whether treatment should be discontinued.

Safety evaluations will also be conducted during the study. Safety evaluations will begin on Day 1 of the study and will continue throughout the study until 28 days after the last dose of study drug, withdrawal of consent, initiation of non-protocol therapy, death, or loss to follow-up, whichever is earliest. Adverse events related to the study medication will be monitored until resolution. The tolerability and toxicity (safety) profile of vemurafenib will be evaluated using the NCI CTCAE, Version 4.0.

The target population includes patients with *BRAF*V600 mutation–positive malignancy (including metastatic melanoma or other cancer types) who were previously enrolled and

treated in an antecedent vemurafenib protocol and did not meet the protocol's criteria for disease progression or are being treated beyond progression and still deriving clinical benefit, as assessed by investigator and may potentially benefit from receiving continued treatment with vemurafenib. Patients with malignant tumor types other than malignant melanoma harboring a V600-activating mutation of *BRAF* who have no acceptable standard treatment options will also be allowed to participate in the trial.

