### **3.2 LENGTH OF STUDY**

Treatment will continue until disease progression (as defined by investigator) or as long as the patient is deriving clinical benefit, as assessed by investigator, if treated beyond progression (case-by-case decision discussed and approved by the Medical Monitor), death, withdrawal of consent, unacceptable toxicity, loss to follow-up, or decision of the Sponsor to terminate the study, whichever occurs first.

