#### **4.1.2 Exclusion Criteria**

Patients who meet any of the following criteria will be excluded from study entry:

1. Adverse event requiring discontinuation of vemurafenib in the antecedent protocol
2. Progressive disease during the antecedent protocol. If approval to treat beyond progression was already given in the antecedent protocol, the patient may roll over into the current protocol without Sponsor's approval. Under special circumstances, when it is felt that the patient may clinically benefit from continued therapy with vemurafenib, enrollment into this protocol and dosing beyond progression may be considered if it is judged by the investigator, in consultation with the Sponsor, to be in the best interest of the patient. All such cases will require approval of the Sponsor before enrolling the patient into this protocol.
3. Meeting any of the following exclusion criterion of the antecedent study at the time the patient is considered for the extension (rollover) study:
  - Current, recent (within 28 days prior to Day 1), or planned use of any anti-tumor therapy outside of this study
  - Any other serious concomitant medical conditions that, in the opinion of the investigator, would compromise the safety of the patient or compromise the patient's ability to participate in the study
  - History of malabsorption or other clinically significant metabolic dysfunctions
  - History of clinically significant cardiac or pulmonary dysfunction as specified in antecedent study

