#### **4.5.3.1 Discontinuation from Study Drug**

Patients may continue to receive treatment with vemurafenib until disease progression (as defined by the investigator, according local institutional standard of care), unacceptable toxicity, or any other discontinuation criterion is met, as follows, whichever occurs first.

- Disease progression as assessed per institutional standards of care
  - Progressive disease during the antecedent protocol. If approval to treat beyond progression was already given in the antecedent protocol, the patient may roll over into the current protocol.
  - Under special circumstances, when it is believed that the patient may clinically benefit from continued therapy with vemurafenib (e.g., in case of mixed progression or progression of single lesion or appearance of a new single lesion), enrollment into this protocol and dosing beyond progression may be considered if it is judged by the investigator, in consultation with the Sponsor, to be in the best interest of the patient. All such cases will require approval of the Sponsor before continuing study drug treatment within this protocol.
- Intolerance of vemurafenib
- If treatment is suspended more than 28 days, the patient should be withdrawn from the study
- Initiation of other cancer medication
- Pregnancy

Patients who discontinue study drug prematurely will be asked to return to the clinic for an end of treatment visit (see Section 4.5.2.4 and Appendix 1). The primary reason for premature study drug discontinuation should be documented on the appropriate eCRF. Patients who discontinue study drug prematurely will not be replaced.

*All patients who discontinue vemurafenib treatment will be followed for safety surveillance per the investigator's discretion.*

Note: New primary melanomas identified as part of the dermatologic risk management plan outlined in Section 4.5.1.9, which are completely excised and without need for additional therapy, do not require patient discontinuation from study treatment.

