## 5.2 SAFETY PARAMETERS AND DEFINITIONS

Safety assessments will consist of monitoring and recording adverse events, including serious adverse events and non-serious adverse events of special interest, measurement of protocol-specified clinical laboratory assessments, measurement of protocol-specified vital signs, and other protocol-specified tests that are deemed critical to the safety evaluation of the study.

Certain types of events require immediate reporting to the Sponsor, as outlined in Section 5.4.

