**Notes:**

Cycle length=28 days; study visits will occur on Day 1 (±3 days, unless otherwise specified) of each cycle through Cycle 7, and then on every other cycle (Cycles 9, 11, 13, 15). Then, for patients still receiving treatment, clinic visits will occur on Day 1 of every third cycle (i.e., Cycles 18, 21, 24, etc.) until unacceptable toxicity or disease progression, as defined by the investigator. Patients who have received a minimum of 17 cycles of vemurafenib treatment in the antecedent study will undergo the screening/baseline visit and then move directly to every-third-cycle study visits commencing with the Cycle 18 visit. *Visits are to be scheduled from screening/baseline visit.*

On the day of scheduled assessments, assessments should be performed prior to study drug dosing, unless otherwise specified.

All required screening/baseline procedures including data collection/transfer from the antecedent study need to be performed after the patient provides informed consent within a maximum window of 15 days from the last day of the antecedent study until treatment start in the extension (rollover) study, except where otherwise indicated.

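### From Cycle 18 on, the protocol ends scheduled clinic visits at disease progression, even for patients kept on vemurafenib after progression

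*Combined protocol and SAP*

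**What the plan says.** **When visits stop.** For patients still on treatment after Cycle 15, the synopsis (Description of Study) and Section 3.1.1 schedule a visit every third cycle "until unacceptable toxicity or disease progression, as defined by the investigator". The notes to Appendix 1 attach the same end to the list of visits: "i.e., Cycles 18, 21, 24, etc.) until unacceptable toxicity or disease progression, as defined by the investigator". Visits in Cycles 1 to 15 carry no such end. Section 4.5.2.4 adds that the visit at which progression is shown serves as the end of treatment visit.

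**When treatment stops.** The primary objective (Section 2.1) covers patients who "are being treated beyond progression and still deriving clinical benefit". Section 3.2 lets treatment run "as long as the patient is deriving clinical benefit, as assessed by investigator, if treated beyond progression", subject to case-by-case approval by the Medical Monitor. For patients who progressed in the antecedent study, Section 4.1.2 says that "enrollment into this protocol and dosing beyond progression may be considered". It also admits, without new Sponsor approval, those already cleared for such treatment. On dosing past progression, Section 4.5.3.1 says: "All such cases will require approval of the Sponsor before continuing study drug treatment within this protocol".

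**When safety evaluation stops.** The synopsis and Section 3.1.1 state that safety evaluations "will continue throughout the study until 28 days after the last dose of study drug", or to consent withdrawal, non-protocol therapy, death or loss to follow-up if earlier. Progression is not on that list. Under Section 5.2 the safety assessments include "measurement of protocol-specified clinical laboratory assessments, measurement of protocol-specified vital signs".

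**The concern.** Treatment and safety evaluation are tied to the last dose, while the late-phase visits are tied to progression. For most patients the two nearly coincide. They separate for a patient who progresses and stays on vemurafenib, a group that the primary objective names.

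For that patient a site following the visit rule would hold no further scheduled visits while the drug is still being taken. At stake is routine on-drug monitoring, and the completeness of the vital-sign and laboratory summaries in Section 6.3. Those summaries serve the secondary objective of describing safety on continued treatment.

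**Working it through.** The plan gives no figure on this point, and Section 6 specifies no hypothesis test. The check is a comparison of rules and a count of visits.

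**1. The rules applied to one patient: in the Cycle 18+ phase, progressed, approved to stay on drug**

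- Treatment (Sections 3.1.1, 3.2, 4.5.3.1): continues.
- Safety evaluation (synopsis, Section 3.1.1): continues to 28 days after the last dose.
- Every-third-cycle visits (synopsis, Section 3.1.1, Appendix 1 notes): ended, because progression has occurred.
- End of treatment visit (Section 4.5.2.4): deemed to have taken place at the progression visit, although treatment has not ended.

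The first two rules cannot be carried out as scheduled if the last two are followed.

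**2. Visits lost**

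Inputs: cycle length 28 days (Section 3.1.1); one visit every third cycle from Cycle 18 (Section 3.1.1, Appendix 1).

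- Interval between visits: 3 × 28 = 84 days.
- Per 84 days on drug after progression: 84 / 84 = 1 visit if the schedule continues; 0 under the literal stop.
- Over 12 cycles: 12 × 28 = 336 days, and 336 / 84 = 4 visits if the schedule continues; 0 under the literal stop.

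The 12-cycle period is only a convenient span. The documents give no duration of treatment after progression.

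**3. Which assessments go with the visit**

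Timed by the visit column of Appendix 1, and so lost under the literal stop:

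- vital signs;
- ECOG status (Section 4.5.1.5 refers its timing to Appendix 1);
- the symptom-directed physical examination, due at subsequent visits (Section 4.5.1.3);
- hematology and serum chemistry. Section 5.1.2.3 (Hepatic Toxicity) requires liver tests during treatment but takes their timing from Appendix 1;
- drug dispensing and accountability.

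Timed by their own rules, which do not end at progression:

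- adverse event reporting (Section 5.3.1);
- ECG (Appendix 1, note f);
- head and neck examination (Section 4.5.1.10; note g);
- dermatology (Section 4.5.1.9; note i);
- chest CT (Section 4.5.1.10; note j);
- urine pregnancy test (note n).

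**The case against.** The best defense is that the phrase is shorthand for the end of treatment. The sentence is about patients still receiving treatment. Its ending also omits death, consent withdrawal and loss to follow-up, so it is hardly a complete stop rule. Section 4.5.3.1 uses similar shorthand and then places the beyond-progression exception under its progression bullet. The Cycle 18+ column of Appendix 1 has no progression stop and includes drug dispensing, so a site could scarcely keep supplying drug without visits. Each such patient is individually approved, and Sections 4.5.2.2 and 4.5.2.3 allow extra tests at any time.

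Much of this stands as evidence of intent: visits were probably meant to continue on drug. It does not remove the conflict. Section 3.2 names progression and then adds treatment beyond it as a separate case, so the protocol writes the exception where it wants one. The visit rule has no exception in any of its three places, and Section 4.5.2.4 points the same way. Extra tests are permitted, not scheduled.

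Four stronger readings may tempt a reader, and the documents do not support them.

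- *That there is a third schedule of a visit every cycle, from Section 5.1.2.2.* Its every-cycle monitoring differs from the visit schedule for all patients after Cycle 7, progressed or not. It is a separate discrepancy and does not belong in the count.
- *That the Appendix 1 notes contradict themselves by sending patients with 17 or more antecedent cycles straight to Cycle 18.* That sentence, like the one in Section 4.5.2.2, sets where visits start and says nothing about when they end.
- *That the 28-day safety rule fails for everyone who progresses.* A patient who stops drug at progression is covered by the end of treatment visit and by adverse event reporting to 28 days after the last dose.
- *That the protocol permits safety monitoring to lapse on drug.* The synopsis and Sections 3.1.1 and 5.2 require it to continue. What is wrong is the visit schedule meant to deliver it.

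**Conclusion.** Wrong as written, but minor. The conflict is confined to patients in the Cycle 18+ phase who are kept on vemurafenib after progression. For them the literal visit rule gives 0 instead of 1 scheduled visit per 84 days, with loss of the assessments timed by the visit column.

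The count rests only on the cycle length and visit interval. It shows what the text says, not what sites have done. The number of affected patients and their time on drug after progression are not given, so the total effect cannot be stated.

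The only listed outcome measure, adverse events and serious adverse events (Section 3.5.2), keeps its own reporting period. The study is descriptive, and no sample size, error rate or other statistical figure is touched. The possible effect on the analysis is missing late vital-sign and laboratory values for this subgroup in the Section 6.3 summaries.

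**What to change.** In the synopsis (Description of Study), Section 3.1.1 and the Appendix 1 notes, replace "until unacceptable toxicity or disease progression, as defined by the investigator" with: *until permanent discontinuation of study drug*.

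In Section 4.5.2.4, state that the progression visit serves as the end of treatment visit only for patients who stop study drug at progression.

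The cost is a few words in four places. No assessment is added beyond those that Appendix 1 already names for treated patients.
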